9.2.8.2. Acute Allergic Reaction

Oral antihistamines (eg, cetirizine and levocetirizine) and/or topical corticosteroids may provide symptomatic relief but effectiveness of these measures has not been established. If treatment with systemic corticosteroids for longer than 24 hours would be required for an acute systemic allergic reaction, the study drugs need to be permanently discontinued.

Management of acute allergic reactions will take into account the protocol-defined procedures outlined in Table 4.

WHO Toxicity Grade	Definitions	Investigator Action
Grade 1	Pruritus suggestive of an allergic reaction without rash	May continue study drugs or have their study drugs discontinued at the investigator's discretion.
Grade 2	Localized urticaria	May continue study drugs or have their study drugs discontinued at the investigator's discretion. Rechallenge is not allowed.
Grade 3	Generalized urticaria, or angioedema	Permanently discontinue study drugs.
Grade 4	Anaphylaxis	Permanently discontinue study drugs.

 Table 4:
 Guidelines for Subjects Developing Allergic Reactions

Grade 1 (Pruritus Suggestive of an Allergic Reaction Without Rash)

Subjects may continue the intake of study drugs or have their study drugs discontinued at the investigator's discretion. Close clinical follow-up is recommended to monitor for any progression of the AE. Subjects should be advised to contact the investigator immediately if there is any worsening of symptoms.

Grade 2 (Localized Urticaria)

Subjects may continue the intake of study drugs or have their study drugs discontinued at the investigator's discretion. Close clinical follow-up is recommended to monitor for any progression of the AE. Subjects should be advised to contact the investigator immediately if there is any worsening of symptoms, in which case the subject will permanently discontinue the study drugs. Rechallenge is not allowed.

Grade 3 (Generalized Urticaria, Angioedema) and Grade 4 (Anaphylaxis)

Subjects will immediately and permanently discontinue the intake of study drugs. Rechallenge is not allowed. Subjects will be treated as clinically appropriate and should be followed until resolution of the AE.

9.2.8.3. Alanine Aminotransferase, Aspartate Aminotransferase, and Bilirubin Elevations

Although an AST and ALT elevation of up to Grade 3 is common in chronic HCV infection due to disease activity, treatment-emergent changes from baseline in ALT and AST levels should be carefully evaluated and results closely monitored with unscheduled study visits, if needed. Isolated and asymptomatic cases (< 1%) of marked elevation of ALT and AST from baseline values have been reported during treatment with AL-335, ODV, and SMV. These reported cases were not accompanied by significant changes in bilirubin or other liver function markers. Increases in bilirubin (both direct and indirect) have been observed during the first weeks of SMV therapy. These bilirubin elevations are caused by a competitive inhibition of biliary transporter systems (OATP1B1) in hepatocytes. Bilirubin elevations following initiation of SMV therapy are typically not associated with increases in ALT or AST levels and rapidly resolve after completion of SMV treatment. Bilirubin elevations have been observed to a much lesser extent with DAA regimens where SMV is administered with RBV.²⁴

Management of treatment-emergent AST, ALT, and/or bilirubin elevations will take into account the protocol-defined procedures outlined in Table 5, Table 6, and Table 7.

1 otar Bini ubin Elevation		
WHO Toxicity Grade	AST or ALT, Ranges	Total Bilirubin, Ranges
Grade 1	\geq 1.25 to \leq 2.5 × ULN	\geq 1.1 to \leq 1.5 × ULN
Grade 2	>2.5 to $\leq 5.0 \times ULN$	>1.5 to $\leq 2.5 \times ULN$
Grade 3	>5.0 to $\leq 10.0 \times ULN$	>2.5 to $\leq 5.0 \times$ ULN
Grade 4	$>10.0 \times ULN$	$>5.0 \times ULN$

Table 5:Treatment-emergent Grade 1 to Grade 4 ALT or AST Elevation and Grade 1 to Grade 4Total Bilirubin Elevation

Key: ALT=alanine aminotransferase; AST=aspartate aminotransferase; ULN=upper limit of normal

Subjects may continue the intake of study drugs at the investigator's discretion in case of Grade 1 and 2 increases in ALT and/or AST and/or Grade 1, 2 and 3 increases in bilirubin levels. In case of a Grade 3 ALT and/or AST increase or if a Grade 4 ALT and/or AST ≤ 2 times the baseline value, this laboratory abnormality must be judged by the investigator to be either "not related" or "doubtfully related" to the study drugs in order to continue the intake of study drugs,

in which case the intake of study drugs may be continued upon agreement with the sponsor. In subjects who continue the study drugs, close clinical follow up is recommended to monitor for any progressive increases.

If a Grade 4 ALT and/or AST value is >2 times the baseline value, a confirmatory measurement should be performed preferably within 72 hours after receipt of the results at the study site. If the Grade 4 value is confirmed to be >2 times the baseline value, the study drugs should be discontinued (Table 6).

In case of a Grade 4 bilirubin elevation, subjects should have a confirmatory measurement within 72 hours after receipt of the results. If the Grade 4 value is confirmed, all study drugs should be discontinued (Table 7).

Subjects should be followed until return to predose baseline value or stabilization of ALT, AST, and/or bilirubin elevation.

WHO Toxicity Grade	Ranges	Investigator Action
Grade 1	\geq 1.25 to \leq 2.5 × ULN	May continue intake of study drugs at the investigator's
Grade 2	>2.5 to $\leq 5.0 \times ULN$	discretion. Monitor for progressive increase in ALT and/or
Grade 3	>5.0 to ≤10.0 × ULN	AST levels.
		In order to continue the study drugs, in case of a Grade 3
		ALT and/or AST increase, this laboratory abnormality should
		be considered "not related" or "doubtfully related" to the
	study drugs. Study drugs may be continued upon agreement	
		with the sponsor.
Grade 4	$>10.0 \times ULN$	May continue study drugs at the investigator's discretion
		(upon agreement with the sponsor) if value is ≤ 2 times the
		baseline value and the event is considered "not related" or
		"doubtfully related" to study drugs. Subjects who continue
		should be carefully evaluated and close follow-up is
		recommended to monitor for progressive increase in ALT
		and/or AST levels.
		If the Grade 4 ALT and/or AST value is >2 times the baseline
	value, a confirmatory measurement should be performed	
		within 72 hours after receipt of the results. If the value is
	confirmed, all study drugs should be discontinued.	

Table 6:	Guidelines for Subjects Developing ALT and/or AST Elevations

Key: ALT=alanine aminotransferase; AST=aspartate aminotransferase; ULN=upper limit of normal

Table 7:	Guidelines for Subjects Developing Bilirubin Elevations
----------	---

WHO Toxicity Grade	Ranges	Investigator Action
Grade 1	\geq 1.1 to \leq 1.5 × ULN	May continue intake of study drugs at the investigator's
Grade 2	>1.5 to ≤2.5 × ULN	discretion. Monitor for progressive increase in bilirubin levels.
Grade 3	>2.5 to $\leq 5.0 \times ULN$	
Grade 4	>5.0 × ULN	A confirmatory measurement should be performed within 72 hours after receipt of the results . If the value is confirmed, all study drugs should be discontinued.

Key: ULN=upper limit of normal

9.2.8.4. Clinical Hepatitis

Subjects should be monitored for any worsening of their hepatic disease and development of overt signs and symptoms (including increased fatigue, malaise, anorexia, nausea, dark urine, clay colored stools, bilirubinemia, jaundice, liver tenderness, hepatomegaly, and severely increased serum transaminase levels).

Subjects with these signs and symptoms must seek medical attention immediately and have their hepatic parameters assessed. If severe worsening of hepatic disease is evident, all study drugs must be discontinued and the sponsor should be contacted.

9.2.8.5. Pancreatic Amylase or Lipase Elevations

For asymptomatic Grade 1, Grade 2, and Grade 3 pancreatic amylase or lipase elevations with no history of treatment-emergent pancreatitis or concomitant lipase increase or signs of pancreatitis, subjects should be carefully evaluated and closely followed. Study drugs may be continued at the discretion of the investigator. In the case of confirmed (within 72 hours) Grade 4 pancreatic amylase or lipase elevations, or the presence of signs consistent with pancreatitis, all study drugs should be interrupted until the diagnosis of pancreatitis is excluded. If pancreatitis is confirmed, all study drugs should be permanently discontinued. An overview of the laboratory ranges to assign grading to a laboratory value for pancreatic amylase and lipase is provided in Attachment 1.

Pancreatitis must be considered whenever a subject develops abdominal pain and nausea, vomiting, or elevated amylase or lipase, and study drugs should be interrupted until the diagnosis of pancreatitis is excluded.

9.2.8.6. Creatine Kinase

Because nucleosides, as a class, have a known risk of mitochondrial toxicity, which is often manifested as muscle injury, this study will systematically assess study subjects for laboratory abnormalities which might be present after muscle injury.

Specifically, CK is checked throughout the study Treatment Period.

Drug-induced myopathy is a diagnosis of exclusion as the differential diagnosis for muscle symptoms can be broad. If a subject develops clinical signs suggestive of muscle injury (eg, proximal weakness and myalgias), a thorough workup (eg, assessment of CK, CK-MB fraction, aldolase, myoglobin, calcium, phosphate, creatinine, and urinalysis) to understand the etiology for the myopathy should be undertaken by a central laboratory.

In all cases where a CK elevation triggers an evaluation of treatment stopping criteria (CK $\geq 3 \times ULN$), or where discontinuation of study drugs is planned due to the suspected muscle injury, the sponsor MUST be notified within 24 hours so that the clinical case and workup and treatment strategy can be discussed.

If a study subject experiences treatment-emergent CK elevations (without a concomitant proportionate CK-MB elevation), the following treatment stopping criteria for CK elevations should be applied³¹:

- In subjects (whether symptomatic or asymptomatic) without a clinical history or a differential diagnosis to suggest etiology of CK elevation (eg, recent exercise, other clinical comorbidities [eg, endocrinal, metabolic disorders] or exposure to medication with known risk of myopathy):
 - If CK is $\geq 20 \times ULN$, immediately redraw and repeat the test. If the repeat remains $\geq 20 \times ULN$, discontinue AL-335. Continuation of ODV and SMV should be discussed with the sponsor on a case-by-case basis.
 - If CK is $\ge 3 <20 \times ULN$, continue study medication. Assess CK, CK-MB every ~72 hours (follow-up assessments) until the CK has normalized (follow-up assessments).
 - If any follow-up CK assessment is \geq 20×ULN, discontinue AL-335. Continuation of ODV and SMV should be discussed with the sponsor on a case-by-case basis.
 - If the third follow-up CK assessment (ie, ~9 days after CK elevation was first recognized) is more than or equal to the prior follow-up CK assessment, discontinue AL-335. Continuation of ODV and SMV should be discussed with the sponsor on a case-by-case basis.
 - If the CK is >1.5×ULN -<3×ULN, consider repeat CK, CK-MB in ~72 hours and continue testing until CK decreases. This might require an unscheduled visit.
- In subjects with a clinical history suggestive of a nonstudy drug related etiology for a CK elevation (eg, recent exercise, other clinical comorbidities [eg, endocrinal or metabolic disorders], or exposure to medication with known risk of myopathy), study medication may be continued. In such instances, the putative cause of the CK elevation should be addressed (eg, stop further exercise or the use of suspect medication) and the CK and CK-MB should be assessed every ~72 hours (=follow-up assessment):
 - If initial CK is <5×ULN, continue study medication unless follow-up CK assessments are increased to ≥20×ULN.
 - If initial CK is ≥5×ULN, continue study drug dosing and assessing follow-up CK and CK-MB every ~72 hours. If the third follow-up CK assessment (ie, ~9 days after CK elevation was first recognized) is more than or equal to the prior follow-up CK assessment, discontinue AL-335. Continuation of ODV and SMV should be discussed with the sponsor on a case-by-case basis.

If CK-MB rises commensurately with elevation of CK, an assessment for cardiac ischemic injury (eg, ECG, troponin) should be initiated.

If a subject who experiences CK elevations also demonstrates clinical or laboratory evidence of renal insufficiency/damage or other clinically significant muscle signs or symptoms (eg, proximal weakness), all study medication should be stopped regardless of the magnitude of the CK elevation.

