10.2. Discontinuation of Study Treatment/Withdrawal from the Study

Discontinuation of Study Treatment

A subject will not be automatically withdrawn from the study if he or she has to discontinue treatment before the end of the treatment regimen.

A subject's study treatment must be discontinued if (see Section 9.2.8 for more details):

- The investigator believes that for safety reasons or tolerability reasons (eg, AE) it is in the best interest of the subject to discontinue study treatment
- The subject becomes pregnant
- The subject has a Grade 4 rash; see Section 9.2.8.1
- The subject has a Grade 3 or 4 allergic reaction; see Section 9.2.8.2
- The subject has a confirmed Grade 4 ALT and/or AST value that is >2 times the baseline value; see Section 9.2.8.3
- The subject has a confirmed Grade 4 bilirubin elevation; see Section 9.2.8.3
- The subject has severe worsening of hepatic disease; see Section 9.2.8.4
- The subject has a confirmed diagnosis of pancreatitis; see Section 9.2.8.5
- The subject has clinical signs suggestive of muscle injury; see Section 9.2.8.6
- The subject has evidence of cardiac toxicity, see Section 9.2.8.7
- The subject has evidence of renal toxicity, see Section 9.2.8.8.

- Clinical Protocol 64294178HPC2003 Amendment 5
- The subject has a Grade 4 AE or a Grade 4 laboratory abnormality at least possibly related to 1 of the study drugs; see Section 9.2.8.9

Note: For laboratory abnormalities triggering treatment discontinuation, see the toxicity management plans described in Section 9.2.8.

- The subject requires treatment with any of the medications reported on the list of disallowed medications; see Section 8.
- The subject meets a treatment stopping rule for viral breakthrough (see Section 6.3)
- One of the study treatment stopping rules is met (see Section 6.4).

If a subject prematurely discontinues study treatment for above-mentioned reasons, he or she will proceed with a Treatment Withdrawal Visit and will subsequently enter the Posttreatment Follow-up Period. Additional unscheduled visits may be performed for safety/tolerability reasons, if needed.

Withdrawal From the Study

A subject will be withdrawn from the study for any of the following reasons:

- Lost to follow-up
- Withdrawal of consent
- Death

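### For CK at or above 3×ULN with clinically significant muscle signs, Section 9.2.8.6 gives conflicting dosing instructions without stating precedence, and Section 10.2 adds a third version

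*Protocol*

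**What the plan says.** Section 9.2.8.6 of the protocol handles treatment-emergent CK elevation without a proportionate CK-MB rise in two branches, followed by two closing paragraphs.

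- **First branch, no alternative explanation.** It begins "In subjects (whether symptomatic or asymptomatic) without a clinical history or a differential diagnosis to suggest etiology of CK elevation". At CK from 3 to below 20×ULN the instruction is "continue study medication. Assess CK, CK-MB every ~72 hours (follow-up assessments) until the CK has normalized". If CK is 20×ULN or more and a repeat confirms it, AL-335 is stopped, and for the other two drugs "Continuation of ODV and SMV should be discussed with the sponsor on a case-by-case basis". AL-335 is also stopped if any follow-up value reaches 20×ULN, or if the third follow-up value is not lower than the one before it.
- **Final paragraph of the section.** If a subject with CK elevation also has renal insufficiency or damage, or "other clinically significant muscle signs or symptoms (eg, proximal weakness"), then "all study medication should be stopped regardless of the magnitude of the CK elevation".
- **Workup sentence, earlier in the section.** "If a subject develops clinical signs suggestive of muscle injury (eg, proximal weakness and myalgias), a thorough workup" is to be done. That sentence does not mention stopping treatment.
- **Sponsor contact.** At CK of 3×ULN or more, or when stopping is planned for suspected muscle injury, the sponsor must be told within 24 hours so that treatment strategy can be discussed.

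Section 10.2 lists the circumstances in which study treatment must be discontinued. One entry reads "The subject has clinical signs suggestive of muscle injury; see Section 9.2.8.6".

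**The concern.** The first branch expressly covers subjects with symptoms and keeps them on treatment in the middle CK range. The final paragraph takes subjects with clinically significant muscle signs off all treatment at any CK level. Proximal weakness is its own example, and it is also an example in the workup sentence. A site that sees a weak subject with raised CK can find a written basis for opposite actions in one section, and a differently worded trigger in Section 10.2.

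Muscle injury is the nucleoside-class risk that the protocol undertakes to monitor systematically, and Section 1.3.2.2 names Section 9.2.8.6 as the management plan for it. The choice of rule decides whether dosing goes on. It also affects how many subjects are recorded as discontinuing for an adverse event. When all drugs are stopped, it fixes the actual end of treatment from which SVR is timed.

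**Working it through.** No formula or power figure is involved. The check is whether one subject can fall under two rules with different actions.

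**Step 1. Compare the rules within Section 9.2.8.6.** The subject has no alternative cause, no proportionate CK-MB rise, and clinically significant muscle signs.

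| CK level | First branch | Final paragraph | Result |
|---|---|---|---|
| >1.5 to <3×ULN | Consider a repeat test in about 72 hours; nothing on dosing | Stop all three drugs | No direct contradiction |
| ≥3 to <20×ULN | Continue all three, retest about every 72 hours | Stop all three drugs | Continue three against stop three |
| ≥20×ULN, confirmed | Stop AL-335; ODV and SMV case by case | Stop all three drugs | Stop one, two left open, against stop three |

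**Step 2. Test with one subject.** Take proximal weakness and CK of 10×ULN (an illustrative value). Since 3 ≤ 10 < 20, the first branch says to continue. Proximal weakness is the final paragraph's own example, so that paragraph says to stop. Both conditions are met and the actions are opposite.

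**Step 3. Look for a tie-breaker.** No sentence says that the final paragraph overrides the branches. The section does not define which symptoms make a subject symptomatic or which signs are clinically significant.

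**Step 4. Add Section 10.2.** Its trigger is signs suggesting muscle injury. It requires neither a CK elevation nor clinical significance. The workup sentence uses nearly the same trigger and asks only for investigation. A subject with myalgia and normal CK is therefore worked up under 9.2.8.6 but listed for mandatory discontinuation under 10.2. The entry in 10.2 refers back to 9.2.8.6, where the conflict is unresolved.

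**Step 5. Size.** On the continue reading, the trend rule first applies at the third follow-up test: 3 × 72 h = 216 h, or about 9 days, as the section itself says. In a cohort of 20, one subject handled differently moves the discontinuation proportion by 1/20 = 5 percentage points. In all 40 subjects it is 1/40 = 2.5 points.

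**The case against.** The best reply is that the final paragraph is meant as an override. It stands outside both branches, adds a further condition, and sets aside CK magnitude, which is what the tiers are built on. A general tiered rule followed by a stricter exception is ordinary drafting. The mention of symptomatic subjects in the first branch would then still make sense, as covering minor symptoms such as mild myalgia. The Section 10.2 entry points the same way. This reading is plausible and may be what the sponsor intends. But precedence is never stated, and the line between minor and clinically significant symptoms, on which the reading depends, is not drawn. Nor does it bring the Section 10.2 trigger into line with the workup sentence.

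The 24-hour notification is a real safeguard, because every direct conflict within 9.2.8.6 lies at CK of 3×ULN or more. It means that sites need not act alone, and that about 9 days of continued dosing should not be taken as the expected outcome. A follow-up value of 20×ULN or more would also stop AL-335 sooner. Still, notification starts a discussion; it does not say which written instruction governs.

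A reader might infer more than the text supports:

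- **That every symptomatic subject is affected.** The final paragraph requires clinically significant signs or symptoms, or renal involvement. Minor symptoms do not clearly trigger it.
- **That the conflict runs through every CK tier.** Below 3×ULN the first branch says only to consider retesting, which is compatible with stopping.
- **That a defined primary measure is distorted.** The primary endpoint in Section 2.1.2 is a general list of safety data. Section 11.4 says only that summaries or narratives may be provided for subjects who stop because of an adverse event.

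**Conclusion.** The point holds in a limited form. For subjects with CK of at least 3×ULN and clinically significant muscle signs or symptoms, Section 9.2.8.6 as written gives conflicting instructions, and Section 10.2 states a third trigger that matches neither the final paragraph nor the workup sentence. The conflict is complete in the range from 3 to below 20×ULN and partial at confirmed values of 20×ULN or more.

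This rests on reading the first branch as it is worded, with symptomatic subjects included, and on there being no statement of precedence. The documents give no rate for this combination of findings, so with about 40 subjects it may never occur. The case for correcting it is that it concerns stopping instructions for a monitored class toxicity and is easy to resolve. It should be corrected, but it does not undermine the trial's design or analysis.

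**What to change.** Reconcile three places: the first branch of Section 9.2.8.6, the final paragraph of that section together with its workup sentence, and the muscle-injury entry in Section 10.2. State which rule takes precedence when more than one applies. Use one consistent term for the triggering muscle signs throughout, with enough definition for a site to apply it. Each combination of CK level and sign or symptom status should then lead to one action.

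A simple split between symptomatic and asymptomatic subjects would not be enough, because the final paragraph turns on clinical significance. The second branch of 9.2.8.6 (suspected cause other than study drug) should be checked in the same edit, since it also allows dosing to continue and does not address muscle symptoms.

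Which action applies in each case is for the sponsor's clinical team. The cost is a wording change in two sections, with no effect on sample size, visits or data collection.

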9.2.8.7. Cardiac Safety Monitoring

Regular cardiac safety monitoring will be done in this study via assessments of AEs, ECGs, and regular echocardiograms.

For all subjects enrolled in this study, LVEF at screening must be $\geq 55.0\%$ (see Section 4.2). Screening echocardiography will not only be used for assessing eligibility but will also be considered as the baseline measurement. Appearance or changes in symptoms or findings in echocardiogram may trigger the following treatment stopping criteria²⁶:

- Asymptomatic patients with no clinical evidence of congestive heart failure:
 - If the absolute decrease from baseline in LVEF is $\geq 10.0\%$ (eg, 59.0% to 49.0%) and resulting in an LVEF of <50.0%, discontinue AL-335, ODV, and SMV.
 - If the absolute decrease from baseline in LVEF is >5.0% and ≤10.0%, or >10.0% and resulting in an LVEF ≥50.0%, an assessment of the subject's clinical status, including symptoms, physical examination, and other clinical parameters should be made before deciding whether to stop or continue study drugs.
- For subjects with symptoms (eg, dyspnea, orthopnea) or signs of congestive heart failure (eg, S3 gallop, pedal edema, pulmonary edema):
 - If the absolute decrease from baseline in LVEF is \geq 5.0%, discontinue AL-335, ODV, and SMV.

For all cases described above, a mandatory assessment and urgent cardiology referral should be initiated. The LVEF decrease must be reported to the medical monitor within 24 hours, so that the clinical case and workup and treatment strategy can be discussed.

The cardiology assessment should include, but is not limited to, the following:

- Review of the cardiopulmonary body systems
- Troponin I assessment
- 12-lead ECG
- Repeat echocardiography (at study approved facility)

Echocardiography must be performed at study approved facility on any subject who develops symptoms or signs of possible congestive heart failure (eg, dyspnea, orthopnea, S3 gallop, pedal edema) during the study, regardless of the timing of such symptoms, including during the Follow-up Period.

For all subjects enrolled in this study, triplicate ECGs will be taken at screening and at regular intervals during the study period. Appearance or changes in symptoms or clinically significant findings in ECG may trigger the following treatment stopping criteria:

- 1. If a 1st degree AV block is diagnosed and
 - a. The PR interval is >200 msec but \leq 240 msec, study drugs can be continued. Close monitoring with weekly ECG is recommended.

- b. The PR interval is >240 msec but ≤300 msec (confirmed by a repeat triplicate analysis at least 30 minutes after the initial assessment), an assessment of the subject's clinical status, including symptoms, physical examination and other clinical parameters should be made and the study drugs can be continued. Close monitoring with weekly ECG is recommended.
- c. The PR interval is >300 msec (confirmed by a repeat triplicate analysis at least 30 minutes after the initial assessment, irrespective of presence or absence of clinical symptoms), ODV must be discontinued. AL-335 and SMV may be continued at the investigator's discretion.
- 2. If a 2nd degree or higher AV block is diagnosed (confirmed by a repeat triplicate analysis at least 30 minutes after the initial assessment and irrespective of presence or absence of clinical symptoms), ODV must be discontinued. AL-335 and SMV may be continued at the investigator's discretion.
- 3. In case the QTc value is >500 msec (confirmed by a repeat triplicate analysis at least 30 minutes after the initial assessment and irrespective of presence or absence of clinical symptoms), ODV must be discontinued. AL-335 and SMV may be continued at the investigator's discretion.

In case the QTc value increases by >60 msec from baseline, thorough evaluation of the clinical case and discussion with the sponsor is required to assess further treatment strategy.

All events described above, should trigger a thorough cardiac assessment (ECG, echocardiography, and cardiology referral) and follow-up (eg, weekly ECG until PR interval is <240 msec). These events as well as any cardiac event that is serious, severe, or life-threatening must be reported to the medical monitor within 24 hours so that the clinical case workup and treatment strategy can be discussed.

